5.0 Study Design

Using a Phase II blinded, randomized placebo-controlled trial, with optional open label extension period, we will evaluate armodafinil's ability to reduce patient-reported fatigue in patients with treated head and neck cancer. This type of trial design is especially important in trials where symptom reduction is the outcome and where knowledge of the treatment arm might bias assessment by the staff or patient. We will purchase commercial grade drug and matching placebo to be dispensed by the investigational pharmacy.

Design: Phase II blinded, randomized placebo-controlled trial, with optional open label extension period

Symptom Intervention Agent: Armodafinil

Study Period: 8-12 weeks depending on participation in the optional open label component : intervention agent daily for 4 weeks (Part I), with continued assessment follow-up period of 4 weeks (Part II). At the end of the 4-week agent intervention, the patient will be given the option to receive open label armodafinil during the 4 weeks follow-up period. If the patient agrees to this option, the follow-up period for these patients will be extended for another 4 weeks.

Primary Symptom Outcome Variable: 4-week (+/- 7 days) area under the curve (AUC) for patient-reported fatigue at its worst (item from the Brief Fatigue Inventory).

Secondary outcomes assessed will include: (1) the 5 most-severe MDASI-HN symptoms at 2-month follow up based on previously collected MDASI-HN data (2) overall MDASI-HN symptom severity, (3) overall MDASI-HN interference, (4) patient-reported alertness (via Epworth Sleepiness Scale), and (5) work productivity and activity impairment questionnaire.

Forty patients will be randomized to either armodafinil or placebo, twenty in each arm. AUC values for patients who drop out of the study after providing 2 weeks of AUC data will be included by carrying their last symptom data forward for the remaining study period under the intent-to-treat rule. The carry-forward method of handling drop-outs will be revisited upon completion of the study to determine if adjustments to these values can be made using longitudinal regression models estimated from patients who completed the entire study.

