6.0 Administration of Pharmacologic Agent

Armodafinil or placebo will begin after enrollment and will continue daily for a total of 4 weeks.

Patients will pick up the assigned study medication at one of the outpatient pharmacy stations in MD Anderson. At pickup, patients will receive instruction on how to take study medications (Appendix EEE). If the patient is unable to pick up the study medication, the investigational pharmacy will mail the study medication to the patient home, overnight.

The participants will take study medication enterally, once daily, in the morning, starting after study entry and continuing for 28 days (4 weeks). The dosing schedule for the symptom intervention agent is described in the table below.

Study medication use will be reviewed at the end of week 4 by study staff. Patients will be asked to bring their study medication to the clinic if they are coming in for a routine visit, at which time study staff will perform a medication count. If the patient is not coming to the clinic at study completion, the medication review will be completed by telephone. Results of the count will be recorded on the Study Medication Accountability form (Appendix K).

During the end of week 4 assessment, the study staff will also offer the participant the option to receive open label armodafinil, at the same dosing schedule described in the table below. If the patient agrees to the optional open label extension, they will either pick-up armodafinil during their routinely scheduled follow-up visit or the pharmacy will mail it to them. A 5-day window will be allowed between the end of Part I and the start of the optional open label extension.

Symptom Intervention Agent	Dosage Forms	Total daily dose: starting day 1 of week 1
Armodafinil or matching placebo	50mg and 100mg capsules or tablets	50 mg the first 3 days, 100 mg the next 4 days, and 150 mg for the remaining treatment period.*

*capsules or tablets, one every morning, may be given without regard to meals. This dosing schedule is to be followed during the 4-week symptom intervention and the optional open label extension.

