The study will accrue 40 patients who will be randomized into 2 arms (armodafinil and placebo), with 20 patients each (see Section 5.0 Study Design). Prior to accruing the first patient, a randomization list will be generated by our biostatistician collaborator from the Department of Biostatistics for all 40 patients, stating to which group a patient was randomized. This list containing the accrual number and treatment group information will be given to Investigational Pharmacy. A sealed backup list will be kept by the assigned data analyst in the Department of Symptom Research. This list will be opened only if unblinding is needed.

Once a patient is enrolled, study staff will inform the Investigational Pharmacy of the patient's accrual number and patient ID. Once a patient is randomized to a treatment arm, the Investigational Pharmacy will retrieve the randomized treatment arm information from the generated randomization list and will relay that information to the dispensing Pharmacy. The patient may visit the most convenient outpatient pharmacy to pick up the study medication assigned.

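### Early dropouts are replaced under an intent-to-treat heading, and carry-forward for later dropouts is reopened at study end with no specified model or adoption rule

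*Combined protocol and SAP*

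**What the plan says.** Section 5.0 defines the primary outcome as the "4-week (+/- 7 days) area under the curve (AUC) for patient-reported fatigue at its worst". Patients who drop out after providing 2 weeks of data are included "by carrying their last symptom data forward for the remaining study period under the intent-to-treat rule". The same paragraph continues: "The carry-forward method of handling drop-outs will be revisited upon completion of the study to determine if adjustments to these values can be made", and says this would be done "using longitudinal regression models estimated from patients who completed the entire study". The study period is "8-12 weeks depending on participation in the optional open label component".

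Section 13.2, in the part headed Intent to treat, requires at least 2 weeks of BFI data to compute an AUC and replaces anyone who drops out sooner. Section 13.23 keeps patients who do not comply with dosing, again under the intent-to-treat rule. Section 13.21 builds the AUC from 8 weeks of scores, not 4.

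In section 9.0, "a randomization list will be generated by our biostatistician collaborator from the Department of Biostatistics for all 40 patients". A sealed backup copy is held by the data analyst: "This list will be opened only if unblinding is needed". Section 13.22 already plans linear mixed models for the secondary outcomes. Section 13.2 says the effect and variability estimates will be used to design the next trial.

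**The concern.** There are two separate faults.

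**Replacement.** A patient who is randomized, starts capsules and leaves in week 1 has no AUC and cannot enter the AUC regression; another patient takes the place. Who is analysed then depends on what happened after randomization, possibly because of treatment. That is not intent to treat, although sections 5.0, 13.2 and 13.23 all use the term. If reasons for leaving differ by arm, the contrast is biased. The list also ends at 40, so a replacement has no pre-generated assignment in the text available.

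**Reopening.** Carry-forward is a clear default, but the plan leaves it open to change once the data are complete. Model form, covariates, missing-data assumption, adoption criterion and which result is primary are all unstated. The sealed list is a partial safeguard, but nothing ties the choice of method to it.

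At stake are the one-sided 5% test in section 13.1 and the estimates handed to the next trial.

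**Working it through.** **Inputs.** From section 13.1: 20 per arm, effect 0.70 SD, equal to 1.7 points, one-sided 5%, 70% power. Assumptions: weekly BFI scores (the assessment schedule appendix is not available) and the dropout patterns stated below, since the documents give none. Negative bias favours armodafinil.

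**The plan's own figure.** Noncentrality = 0.70 × √(20/2) = 2.21. The one-sided t test with 38 df has power 70.2% (71.5% by normal approximation). The stated 70% reproduces and is not in dispute. Implied AUC SD = 1.7/0.70 = 2.43; standard error (SE) of the contrast = 2.43 × √(2/20) = 0.77.

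**Replacement, by formula.** Suppose there is no true effect and only armodafinil patients leave early. Let a share q leave who would have scored k SD worse than their arm's mean. Those remaining are shifted by qk/(1-q). At q = 10% and k = 0.5 to 1.0 this is 0.056 to 0.111 SD, or 0.13 to 0.27 points, and the one-sided error becomes 7.1% to 9.8%.

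**Replacement, by simulation.** AR(1) correlation 0.7, normal scores, true contrast -1.7, leaving after week 1 with logit p = a + b × (week-1 score as deviation from the placebo mean):

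| Early leaving | Bias (points) | In SE |
|---|---|---|
| Armodafinil 17% (a = -1.2, b = 0.45), placebo 5% unrelated to score | -0.38 | 0.49 |
| Armodafinil 10% (a = -2.0, b = 0.45), placebo 5% unrelated | -0.22 | 0.29 |
| Armodafinil 17% (a = -1.3, b = 0.2), placebo 5% unrelated | -0.20 | 0.26 |
| Unrelated to score, 17% vs 5% | 0.00 | 0 |
| Same rule in both arms (a = -2.0, b = 0.45): 10% vs 18% | +0.17 | 0.22 |

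These runs need a per-visit SD of about 3.0 on a 0-10 item whose entry criterion excludes scores of 4 or less. With baseline held to 5-10, scores clipped to 0-10 and a latent mean of 6 (assumed), the first case falls to about -0.22, or 0.38 SE, because the AUC SD drops to 1.82.

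**Carry-forward.** Weekly trapezoid weights over 4 weeks are 1/8, 1/4, 1/4, 1/4, 1/8. For a patient last seen at week 2, that score's weight rises from 25% to 25 + 25 + 12.5 = 62.5%. Let s be natural recovery per week and r the rebound on stopping armodafinil. Carry-forward minus truth (counting off-drug scores) is 0.25s + 0.125 × 2s - 0.375r = 0.5s - 0.375r, with r = 0 on placebo.
- r = 1.7, dropout 30% vs 10%: 0.30 × (-0.375 × 1.7) = -0.19, which is 0.25 SE.
- s = 0.5, dropout 30% vs 10%: 0.20 × 0.25 = +0.05.

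The flat-course assumption deserves some care. The schedule is "50 mg the first 3 days, 100 mg the next 4 days, and 150 mg for the remaining treatment period", so a week-2 rating follows only about one week at the last step. Over the 8-week window the formula is 2.25s - 0.6875r, and the same two cases give -0.35 and +0.23, ignoring open-label use.

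**Reopening.** 6000 null trials; dropout after week 2 of 20/20, 30/10 and 30/30%; adjustment by completers-only regression on arm and weeks 0-2 with single imputation; Monte Carlo SE 0.3 points.

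| Window | Imputation alone | Better of the two results |
|---|---|---|
| 4 weeks | 5.3, 5.4, 6.3% | 5.7, 5.7, 6.7% |
| 8 weeks | 6.4, 6.7, 8.6% | 6.9, 7.2, 9.6% |

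Choosing adds 0.3 to 1.0 percentage points. The rest of the excess, most of it at 8 weeks, comes from single imputation understating variance.

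**List length.** 40/0.9 = 44.4, so 45; 40/0.8 = 50. These are averages: P(Bin(45, 0.9) ≥ 40) = 71% and P(Bin(50, 0.8) ≥ 40) = 58%. For about 95% assurance, 48 and 56 entries are needed.

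**The case against.** The strongest reply is that this is a small phase II trial meant to estimate effects, that it is blinded, and that every size above rests on assumed dropout. Much of that stands. The biases are about half a standard error or less, and zero if leaving is unrelated to fatigue. The conflict between replacement and the intent-to-treat label, however, needs no dropout assumption, and a biased estimate would pass into the next trial's design.

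A reader might infer four stronger things that the documents do not support:
- That the method will be chosen with treatment codes open. The text does not say so, and the sealed list points the other way.
- That no model is named. Section 5.0 names longitudinal regression and its fitting set; what is missing is the specification.
- That dropouts' observed scores are thrown away. They are left out only when the coefficients are estimated; they remain in those patients' AUCs and can serve as predictors.
- That the plan is tilted towards armodafinil. The sign depends on who leaves, and one plausible pattern goes the other way.

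A mixed model is also no cure-all. In the 17% vs 5% case its simulated bias is -0.017, but only because leaving depends solely on an observed score and the truth is defined as if leavers stayed on drug. If off-drug rebound of 1.7 counts, a further 0.625 × 1.7 × 0.17 = 0.18 appears, giving about -0.20. For later dropout under rebound it matches carry-forward (-0.129 vs -0.128), and with recovery added it is worse (-0.126 vs -0.078). Most of its precision gain comes from baseline adjustment: root mean squared error is 0.837 for the plan, 0.602 with a baseline covariate and 0.561 for the mixed model.

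**Conclusion.** The point holds and should be fixed, but the expected harm is modest. Replacing early dropouts contradicts the intent-to-treat label and leaves replacements without a stated assignment. The missing-data method for the primary outcome is not settled in advance.

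Replacement matters most: illustratively from about -0.4 to +0.17 points against a target of 1.7, in either direction, and smaller on a bounded scale. Carry-forward over 4 weeks is a minor problem, and freedom to choose between methods adds about one percentage point of error at most. These sizes assume weekly scores, an AUC SD of 2.43 and dropout patterns that the documents do not supply. The textual conflict assumes none of this, and the stated power is unaffected.

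**What to change.** Before unblinding:

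1. In section 13.2, strike the replacement rule. State that all randomized patients stay in the analysis, and that any extra patients are added to them and do not substitute for them. Generate the longer list in advance: at least 45 entries at 10% early dropout and 50 at 20%, with a margin (48 and 56 give about 95% assurance of 40 patients with 2 weeks of data).
2. Delete the reopening sentence in section 5.0. Name one primary method in section 13: a mixed model for repeated measures on all observed worst-fatigue scores from all randomized patients. Include arm, time, arm-by-time and baseline, with unstructured covariance and a named fallback such as heterogeneous AR(1). The AUC contrast is a linear combination of visit means. State the missing-at-random assumption.
3. Keep carry-forward as a sensitivity analysis. Add one missing-not-at-random analysis that shifts armodafinil dropouts' unobserved scores in steps up to 1.7 points. Each point moves the 4-week contrast by 0.375 × the share leaving after week 2, or 0.625 × the share leaving after week 1. Include patients with only a baseline score, who add nothing to a model that uses baseline as a covariate.
4. Reconcile the AUC window between sections 5.0 (4 weeks) and 13.21 (8 weeks), so that the period over which scores are carried forward is defined. Open-label armodafinil is offered after week 4.

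The cost is wording in sections 5.0, 13.2 and 13.21, a longer list and slightly more analysis. No visits are added, and no more patients than replacement already implies. The downside is reliance on missing at random, which does not remove bias from rebound after stopping drug; item 3 is there for that reason.

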A list of adverse events (AEs) known to be associated with primary treatment is listed in section 4.0 of the protocol. Study staff will monitor for AEs via telephone contact with the subjects using the Phone Contact Form according to the Assessment Schedule. In addition, study participants will be able to contact study personnel via a telephone hotline, and study participants can be seen by study personnel at MD Anderson if there are any concerns or questions regarding potential side effects. If seen in person by study personnel, clinical monitoring form will be completed. Also, if study subjects are coming to MD Anderson for

routine clinical follow up (visits unrelated to this study), they will be seen by study staff as frequently as weekly during the study period, and the clinical monitoring form will be completed every time.

Patients will be advised to discontinue drug at first sign of body rash during this study and to immediately notify study personnel, who will in turn notify the PI for appropriate medical management.

All grade 3 and 4 toxicities reported by patients in this trial will be evaluated by the principal investigator in consultation with the treating physician, or by another attending physician if the PI is not available, to determine whether the toxicities were possibly caused by the study medication (rather than being effects from previous cancer therapy). The investigators will discriminate between expected dermatitis related to radiation therapy or chemotherapy versus armodafinil hypersensitivity. If 1 or more armodafinil-related grade 3 or 4 toxicities is observed in the patients assigned to armodafinil, the study will be terminated.

The interaction screening will be the responsibility of the research staff. Study exclusion criteria of known drug interactions and drugs that would require additional monitoring if given in conjunction with armodafinil will also be in place for patient safety. The research staff will review any current or new patient medications prior to initiating treatment, and will document all medications patients have used or will use during the trial. During the trial, the research staff will capture any potential drug interactions that could cause an AE on the Adverse Event forms. Medication sheets will be provided to both patients and treating physicians to inform them of the possibility that the patients may be receiving armodafinil (see Appendix EEE and EE).

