11.0 Adverse Event Reporting

11.1 Adverse Events (AE) (Appendix I)

Telephone monitoring will be conducted by study staff weekly over the entire study period. Patients can contact study staff at any time during study period through the study hotline with questions or concerns regarding potential side effects of study medication. In addition, patients can be seen by either the treating physician or the PI as needed.

Treatment-related toxicities (NCI Common Terminology Criteria for Adverse Events, version 4) will be monitored by both clinic and research staff weekly either by phone or during any regular clinical appointments as described above. Other clinical variables will be collected as described in the Assessment Schedule. (Appendix X - AE Form).

Expected (due to previous cancer treatment or symptom treatment) or unrelated grade 1 or 2 toxicities will not be reported. AEs that are grade 3 and above that are definite, probable, or possible and related will be reported. AEs will be tabulated and reported as a summary on the continuing review report. All grade 3 and 4 toxicities will be evaluated by the PI and treating physician to determine if the toxicities were due to study medication.

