11.2 Serious Adverse Events (SAE) (Appendix J)

A serious adverse event is any adverse drug experience occurring at any dose that results in any of the following outcomes:

- Death.
- A life-threatening adverse drug experience – any adverse experience that places the patient, in the view of the initial reporter, at immediate risk of death from the adverse experience as it occurred. It does not include an adverse experience that, had it occurred in a more severe form, might have caused death.
- Inpatient hospitalization or prolongation of existing hospitalization.
- A persistent or significant disability/incapacity – a substantial disruption of a person's ability to conduct normal life functions.
- A congenital anomaly/birth defect.

Important medical events that may not result in death, be life-threatening, or require hospitalization may be considered a serious adverse drug experience when, based upon appropriate medical judgment, they may jeopardize the patient or subject and may require medical or surgical intervention to prevent one of the outcomes listed in this definition. Examples of such medical events include allergic bronchospasm requiring intensive treatment in an emergency room or at home, blood dyscrasias or convulsions that do not result in inpatient hospitalization, or the development of drug dependency or drug abuse (21 CFR 312.32).

Important medical events as defined above, may also be considered serious adverse events. Any important medical event can and should be reported as an SAE if deemed appropriate by the PI or the IND Sponsor, The University of Texas MD Anderson Cancer Center Institutional Review Board system (UTMDACC IRB) .

All events occurring during the conduct of a protocol and meeting the definition of a SAE must be reported to the IRB in accordance with the timeframes and procedures outlined in "The University of Texas MD Anderson Cancer Center Institutional Review Board Policy on Reporting Serious Adverse Events". Unless stated otherwise in the protocol, all SAEs, expected or unexpected, must be reported to UTMDACC IRB, regardless of attribution (within **5 working days** of knowledge of the event).

All life-threatening or fatal events, expected or unexpected, and regardless of attribution to the study drug, require a written report to be submitted within **24 hours** (next working day) of knowledge of the event to the Safety Project Manager in UTMDACC IRB .

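### The study-termination rule covers only patients assigned to armodafinil, so a drug-related grade 3 or 4 toxicity in a placebo-assigned patient taking open-label armodafinil would not trigger it as written

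*Combined protocol and SAP*

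**What the plan says.** **Termination rule (Section 5.0).** A single armodafinil-related toxicity of grade 3 or 4 is enough: once one is "observed in the patients assigned to armodafinil, the study will be terminated". Three conditions must hold together: the event is judged related to armodafinil, it is grade 3 or 4, and the patient was assigned to armodafinil. No other section states a rule for stopping the study. Section 12.0 covers removal of individual patients, and Section 11.0 covers monitoring and reporting.

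**Open-label option (Sections 5.0 and 6.0).** After the four blinded weeks, "the patient will be given the option to receive open label armodafinil during the 4 weeks follow-up period". Section 6.0 repeats the offer at the week 4 assessment. Neither section restricts it by randomized arm.

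**Causality review.** Section 5.0: "All grade 3 and 4 toxicities reported by patients in this trial will be evaluated by the principal investigator". Section 11.1: "All grade 3 and 4 toxicities will be evaluated by the PI and treating physician to determine if the toxicities were due to study medication". Both name grades 3 and 4. Neither is limited to one arm.

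**Reporting.** Toxicity is graded by the "NCI Common Terminology Criteria for Adverse Events, version 4". Section 11.1 sets the reporting threshold: "AEs that are grade 3 and above that are definite, probable, or possible and related will be reported". Section 11.2 adds: "All life-threatening or fatal events, expected or unexpected, and regardless of attribution to the study drug, require a written report", due within 24 hours. Neither provision is linked to termination.

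**The concern.** The rule protects patients from armodafinil, but it is defined by randomized arm rather than by exposure to the drug. Once placebo-assigned patients may take open-label armodafinil, the two no longer coincide. The same related grade 3 or 4 toxicity on open-label drug would end the study if the patient had been randomized to armodafinil and would not if the patient had been randomized to placebo. In open label everyone knows what the patient is taking, yet applying the rule would turn on a blinded assignment that Section 9.0 keeps on a sealed backup list.

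The uncovered patients are also new starters. Section 4.70 says that most serious rashes with modafinil were reported in the first 5 weeks after starting treatment. A placebo patient's 4 open-label weeks fall inside that window.

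A smaller question concerns grade. The rule uses a closed range, while the reporting threshold in Section 11.1 and the rash removal criterion in Section 12.14 are open-ended from grade 3 upward.

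**Working it through.** The plan gives no operating characteristic for the rule, so there is no figure to reproduce. The check is a comparison of texts followed by an illustration.

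**1. Population.**
- Covered by the rule as worded: 20 patients (armodafinil arm, Sections 5.0 and 13.1).
- Could take armodafinil on study: 20, plus between 0 and 20 placebo patients who opt in, so 20 to 40.
- Outside the rule: up to 20 of 40, or 50%, if every placebo patient opts in.
- Section 9.0 takes the treatment group from the randomization list. Open-label drug is something the patient chooses to receive. Assignment therefore most naturally means the randomized arm.

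**2. Chance that the gap matters.** The documents give no rate of related grade 3 or 4 toxicity. Assume a rate p per exposed patient, equal in all exposed patients and independent between them. With m placebo crossovers:
- At least one event among crossovers: A = 1 − (1 − p)^m. This ignores the armodafinil arm and is an upper bound.
- At least one event among crossovers and none in the 20 armodafinil-arm patients, so that the rule never fires: B = A × (1 − p)^20.

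For m = 20:
- p = 2%: (0.98)^20 = 0.668; A = 0.332; B = 0.332 × 0.668 = 0.222.
- p = 5%: (0.95)^20 = 0.358; A = 0.642; B = 0.642 × 0.358 = 0.230.

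For m = 10:
- p = 2%: A = 1 − (0.98)^10 = 0.183; B = 0.183 × 0.668 = 0.122.
- p = 5%: A = 1 − (0.95)^10 = 0.401; B = 0.401 × 0.358 = 0.144.

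Over a wider range of p, with m = 20:

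| Assumed p | A (upper bound) | B (rule never fires) |
|---|---|---|
| 0.5% | 0.095 | 0.095 × 0.905 = 0.086 |
| 1% | 0.182 | 0.182 × 0.818 = 0.149 |
| 2% | 0.332 | 0.222 |
| 5% | 0.642 | 0.230 |
| 10% | 0.878 | 0.878 × 0.122 = 0.107 |

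With m = 20, B has the form x(1 − x), so it cannot exceed 25% at any rate. If an armodafinil-arm event came only after a crossover event, the rule would have been silent for a time, so the relevant figure lies between B and A.

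**3. Grade range, side by side.**
- Termination (5.0): grades 3 and 4.
- Causality review (5.0 and 11.1): grades 3 and 4.
- AE reporting (11.1): grade 3 and above.
- Removal of a patient for rash (12.14): grade 3 or higher.
- Fatal events (11.2): written report, with no link to termination.

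The documents do not define a grade above 4. Taking it to be a fatal event, as the open-ended ranges imply, the rule and the causality review do not name it. A death preceded by a recorded related grade 3 or 4 toxicity in the armodafinil arm would already have fired the rule. What remains is a related event first recorded as fatal.

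**The case against.** The strongest reply is that these patients are not unprotected. Causality review covers toxicities in all trial patients, weekly monitoring runs through the entire study period, and SAEs are captured until 30 days after the last dose. The removal criteria in Section 12.0 and the instruction to stop at the first sign of rash apply whatever the arm. The IRB or the principal investigator could act outside the written rule. All of this stands. It shows that the events would be seen, but it does not make the termination rule apply to them.

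A second reply is that the rule was written to separate active from placebo in the blinded comparison and simply did not consider open label, or that assignment can be read loosely to include open-label use. The omission is probably unintended. Even so, a rule that ends a trial should not depend on a loose reading when Section 9.0 ties the treatment group to the randomization list.

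A third reply concerns size. The rates are assumptions, and full crossover is the extreme case. If all patients in both arms opted in, the uncovered share of drug time would be 20 × 4 of (20 × 8 + 20 × 4) patient-weeks, that is 80/240 or 33%, rather than 50%. This is fair, and the figures should be read as illustrations.

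Three stronger readings are tempting, and the documents do not support them.
- A reader might infer that any event in a placebo-assigned patient escapes the rule. The rule acts only on related grade 3 or 4 toxicities, so most events would not trigger it in either arm.
- A reader might infer that Section 11.1 contradicts Section 5.0 on grade. Its open-ended range is a reporting threshold, and its causality sentence uses the same grades 3 and 4 as Section 5.0.
- A reader might infer that the plan lets the study carry on after any drug-related death. The literal gap is limited to a related event first recorded as fatal, and such an event must be reported within 24 hours.

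**Conclusion.** The population gap holds on the plain text: the rule follows randomized arm, the open-label option does not, and nothing in Sections 6.0, 9.0, 11.0 or 12.0 joins them. Followed literally, the rule gives different answers to the same drug-related event. It leaves out up to 20 of up to 40 exposed patients.

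At assumed rates of 2% or 5%, the chance that such an event occurs and the rule never fires is about 22% or 23% with 20 crossovers, and 12% or 14% with 10. The values 33% or 64% (18% or 40% with 10 crossovers) are upper bounds. All of these rest on rates not in the documents, on equal and independent risk per exposed patient whatever the length of exposure, and on the assumed number of crossovers. The textual finding depends on none of them.

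The grade point is secondary. It is a gap in wording, not a direct contradiction.

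**What to change.** Revise the sentence in Section 5.0 so that:
- the population of the rule is reconciled with the open-label option in Sections 5.0 and 6.0, stating whether it means the randomized arm or all patients exposed to armodafinil in either part; and
- its grade range, and the range for causality review in Sections 5.0 and 11.1, are reconciled with the reporting range in Section 11.1, so that the handling of a related event first recorded as fatal is explicit.

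Which patients, grades and number of events should stop the study is for the clinical team to decide. The cost is about one sentence, with a matching edit in Section 11.1 if the causality range changes. No new data are needed, because toxicities are already monitored weekly.
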